1. SPECIFIC AIMS

Aim 1: Map the cellular and synaptic targets of cervical electrical stimulation (CES).

CES circuit interactions at both the spinal and supraspinal levels will be characterized using a common structure comprising an electrical or magnetic conditioning stimulus followed by a test stimulus delivered at a range of intensities, sites, and interstimulus intervals (ISI). This will shed insight into which circuits CES activates, and how CES circuits interact with circuits activated by other exogenous neural stimuli.

Hypothesis 1.1: Conditioning CES will potentiate spinal motor neuron responses to test TMS pulses. Depending on the timing of the effect, this would support the mechanism of heterosynaptic summation between segmental Ia input and descending corticospinal input¹, or sensory cortical facilitation of motor cortex excitability²⁻⁴, or both.

Hypothesis 1.2: Conditioning CES will increase persistence of spinal motor neuron F-responses to retrograde stimulation over the median and ulnar nerves. This would further establish that CES could modulate motor neuron excitability at the segmental level.

Hypothesis 1.3: Conditioning subthreshold CES will reduce spinal motor neuron H-responses to afferent stimulation over the median nerve. This would indicate the potential for CES to reduce hyperactive muscle stretch responses (spasticity) via homosynaptic interactions.

Aim 2: Determine optimal CES parameters for acutely facilitating concurrent wrist and hand movements.

Volitional limb movements depend on the same corticospinal and motor neuron circuits as those activated by TMS and F-waves. Therefore, if CES facilitates TMS and/or F-responses, CES may also be able to facilitate volitional limb movements. The experiments in Aim 2 will shed light on this clinically relevant question.

Hypothesis 2.1: Subthreshold CES will *facilitate* concurrent wrist and hand muscle activation, supporting CES's ability to positively modulate corticospinal and/or motor neuron excitability. This would present an opportunity to directly translate this paradigm for clinical benefit by combining repetitive subthreshold CES with repetitive task-oriented physical exercise training.

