- Interpretation: If subthreshold CES facilitation occurs at ISI between 2-20 ms, this would support the mechanism of heterosynaptic summation between segmental Ia input and descending corticospinal input¹. If facilitation occurs at ISI between 20-60 ms, this would support the mechanism of sensory cortical facilitation of motor cortex excitability (based on analogous findings using peripheral nerve stimulation^{4,2,3}). Because TMS travels along the same corticospinal and subcortical circuits used during volitional movement, this would also set the basis for using subthreshold CES to facilitate motor

responses during physical training programs (see Aim 2). Subjects with incomplete cervical SCI are expected to have reduced CES-TMS facilitation compared to uninjured subjects (see **Figure 4**).

CES-peripheral nerve interactions:

- Goal: Measure interactions between afferent and efferent cervical nerve roots, segmental interneuronal circuits, orthodromically conducting peripheral sensory fibers, and antidromically conducting peripheral motor fibers.
- Methods: F-wave pulse intensity will be ~110-120% of the intensity that results in maximal compound motor action potential (CMAP). H-reflex pulse intensity will be calibrated to result in H-reflex amplitude ~20-25% of maximal CMAP⁶³. Conditioning CES pulse intensity will be set between 30-175% of motor threshold, delivered within 300 ms of test pulses. For subthreshold conditioning CES, either single or “theta bursts” (3 pulses at 50 Hz)¹⁹ will be delivered. All pulse combinations will be delivered at a rate of 0.1 Hz, in pseudorandom parameter order, until 8 (CES-H combinations) or 25 (CES-F combinations) responses per parameter have been recorded.
- Hypothesis 1.2: Conditioning CES will increase persistence (number of responses per 25 stimuli) of median (APB) and ulnar (FDI) F-responses elicited up to 50 ms later.
- Hypothesis 1.3: Conditioning CES will reduce amplitude of median (FCR) H-responses elicited up to 50 ms later.
- Speculative hypothesis 1.2: Conditioning suprathreshold CES will block spinal motor neuron F-responses delivered up to 10 ms later.

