- Interpretation: These experiments will lead to multiple insights. Through segmental interactions, confirmation of Hypothesis 1.2 would further demonstrate the ability of CES to positively modulate motor neuron excitability, and confirmation of hypothesis 1.3 would indicate the potential for CES to reduce spasticity⁴⁵. Confirmation of speculative hypothesis 1.2 would demonstrate that at high intensity, CES pulses travel via efferent nerve roots and collide with retrogradely traveling F-waves.

Aim 1 data analysis: Peak-to-peak amplitude of all conditioned pulses will be normalized to the amplitude of unconditioned pulses. For each interaction paradigm, analysis of variance (ANOVA) with factors of subject group, stimulus intensity, interstimulus interval, and muscle will be performed. Post hoc pairwise comparisons will be made using Tukey’s method. *Power:* Using a conservative predicted effect size of 0.4 for each interaction paradigm, >80% power will be achieved with a sample size of 10 for each analysis (repeated measure ANOVA) with four factors. 15 subjects in each group (SCI, able-bodied) will undergo testing.

Aim 1 Timeline (Table 2):

Each subject will undergo three testing sessions on separate days, with a minimum of 24 hours and a maximum of two weeks between visits. Per subject, Aim 1 participation would therefore take 3 to 28 days. 30 subjects will be enrolled, resulting in 90 total testing sessions. A conservative projection of completing two testing sessions per week would result in a timeline of 45 weeks or 11-12 months for completing Aim 1.

Aim 2: Determine optimal CES parameters for acutely facilitating concurrent wrist and hand movements.

Volitional limb movements depend on the same corticospinal and spinal motor circuits as those activated by TMS and F-waves. Therefore, since preliminary data shows that subthreshold CES facilitates TMS responses, CES may also be able to facilitate volitional limb movements. The experiments in Aim 2 will shed light on this clinically applicable question.

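### Aim 1 normalises amplitudes to the unconditioned response but states no test against it, so the planned ANOVA and Tukey p-values do not by themselves test potentiation, reduction or its interval window

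*Combined protocol and SAP*

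**What the plan says.** The hypotheses are in Section 1 (Specific Aims) and again in Section 3 under CES-TMS interactions and CES-peripheral nerve interactions. Hypothesis 1.1 predicts a larger response to TMS after conditioning CES. Its mechanism is to be read from timing: "Depending on the timing of the effect, this would support the mechanism of heterosynaptic summation" or sensory cortical facilitation, or both. Section 3 gives the windows: "If subthreshold CES facilitation occurs at ISI between 2-20 ms, this would support the mechanism of heterosynaptic summation" and "If facilitation occurs at ISI between 20-60 ms, this would support the mechanism of sensory cortical facilitation of motor cortex excitability". Hypothesis 1.3 predicts a smaller H-response: "Conditioning CES will reduce amplitude of median (FCR) H-responses elicited up to 50 ms later". Hypothesis 1.2 predicts higher F-wave persistence, defined as the percent of positive responses out of 25 pulses. A speculative companion predicts that suprathreshold CES blocks F-responses up to 10 ms later.

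The Aim 1 data analysis paragraph has three parts. Amplitudes are scaled: "Peak-to-peak amplitude of all conditioned pulses will be normalized to the amplitude of unconditioned pulses". Then, for each paradigm, "analysis of variance (ANOVA) with factors of subject group, stimulus intensity, interstimulus interval, and muscle will be performed", followed by Tukey post hoc pairs. Power is stated as above 80% at a sample size of 10: "Using a conservative predicted effect size of 0.4 for each interaction paradigm". Fifteen subjects per group will be tested.

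Conditioning intensities in Aim 1 run from 30% to 95% of motor threshold (TMS) or 30% to 175% (peripheral nerve). A 0% sham pulse is named only in Aim 2.

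**The concern.** Each hypothesis compares conditioned with unconditioned responses. After normalising, hypothesis 1.1 becomes a ratio above 1 and hypothesis 1.3 a ratio below 1. The stated ANOVA asks something else: whether conditioned cells differ from one another across group, intensity, ISI or muscle. A CES effect of equal size at every ISI gives no ISI effect to detect. A significant ISI term may reflect facilitation at some ISIs or suppression at others.

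Suppression is not far-fetched here. Section 2 cites inhibition of a second spinal pulse at 20-50 ms, and of paired TMS pulses at 1-3 and 100-200 ms. The normalised means will show direction. But the confirming test, its window, the intensities pooled and the multiplicity rule would be chosen after the data are seen, and the mechanism is read from that choice.

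**Working it through.** **1. The plan's own power figure.** From the Aim 1 data analysis: effect size 0.4, n = 10, repeated-measures ANOVA. Not stated, so assumed: 0.4 is Cohen's f, alpha 0.05, one group, m = 4 measurements, correlation ρ = 0.5.
- λ = f²·n·m/(1−ρ) = 0.16 × 10 × 4/0.5 = 12.8, with 3 and 27 degrees of freedom. Power is 80.6%, which agrees with the stated figure.
- With other unstated inputs, power runs from 36% (m = 2, ρ = 0) to 99.9% (m = 8, ρ = 0.7).
- The figure concerns differences among factor levels.

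**2. What F and Tukey can see.** Multiply every ratio by c. All sums of squares are multiplied by c², so F is unchanged. Tukey's statistic, (mean_i − mean_j)/√(MSE/n), has numerator and denominator both multiplied by c, so it is unchanged too.
- Pattern A: ratio 1.3 at 2-20 ms and 1.0 elsewhere (facilitation only).
- Pattern B: A divided by 1.3, that is 1.0 at 2-20 ms and 1/1.3 = 0.77 elsewhere (suppression only).
- A and B give the same F and the same Tukey p-values. Only A supports hypothesis 1.1.
- If normalised means percent change, 100 × (ratio − 1), the subtraction does not alter F or Tukey either.

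**3. Simulation.** From the documents: 15 + 15 subjects, 8 pulses per condition. Assumed: lognormal pulses; trial coefficient of variation (CV) 0.7; 10 ISIs (4 in 2-20 ms, 3 in 20-60 ms, 3 later); 3 intensities; 2 muscles; between-subject log-SD of the CES effect 0.3; no extra subject-by-window variation. The direct test is a one-sample t test on each subject's window-mean log ratio, with Holm over two windows.
- Uniform 1.3-fold facilitation: the ISI F rejects in 4%, the direct test in 97%.
- Patterns A and B: the ISI F rejects in 100% for both. Over CV 0.3-1.0 and window SD 0-0.15, the direct test flags A upward at 2-20 ms in 85-99% of runs, and B downward at 20-60 ms in 86-99%.
- No effect: the direct test flags either window in 3-4%.

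A second simulation used 6 ISIs, between-subject SD 0.25 and within-subject SD 0.30 on the ratio scale, n = 30. A uniform ratio of 1.5 gave F 5.7%, Tukey 5.2%, test against 1 100%. A uniform 0.6 gave 5.1%, 4.9% and 100%. Suppression to 0.7 at one ISI, with no facilitation anywhere, made F reject in 98.3% and Tukey in 98.5%.

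**4. Adding unconditioned after normalising.** That cell equals 1 for every subject and has no variance, so the pooled error term is wrong for contrasts with it. Their error rate in the second simulation was 1.2% (between-subject SD 0.25) or 8.4% (SD 0.60), not 5%.

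**5. Power for one conditioned-versus-unconditioned contrast** (two-sided 5%, before multiplicity; noncentral t with δ = d√n).
- If f = 0.4 with two levels and ρ = 0.5, d = 2 × 0.4 = 0.8. Then δ = 2.53, 3.10 and 4.38, and power is 62%, 82% and 99% at n = 10, 15 and 30.
- If 0.4 is d itself, δ = 1.26, 1.55 and 2.19, and power is 21%, 30% and 56%.

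**The case against.** The analysis paragraph lists factors but not their levels, and unconditioned pulses are plainly recorded, so the investigators may intend such a level or an intercept test. Both are possible and neither is written. Step 4 shows that the level would not work cleanly after normalising. An intercept test would meet the overall question but not the window question.

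ISIs reach 300 ms, so early-against-late contrasts read beside the means are informative. This stands in part: late ISIs act as a control only if CES does nothing there, which the protocol does not assume. The group term also does address the reduced facilitation expected in SCI.

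The scale argument does not extend to persistence, which is not normalised and could carry an unconditioned level in the ANOVA. This stands in full; for persistence the comparison is only unstated.

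The power of the direct test is optimistic if facilitation is smaller in SCI or confined to part of a window. This stands, and the lower figures are given as a cost of the change.

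A reader might infer that Aim 1 cannot answer its hypotheses, or that 15 per group is too few. The documents support neither. The unconditioned data are collected, and under the Cohen's f reading the enrolled numbers give 82% (one group) or 99% (both) for a single unadjusted contrast.

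**Conclusion.** The point holds as a gap in the stated analysis and should be fixed before the data are analysed. Followed as written, the ANOVA and Tukey p-values on normalised amplitudes do not test potentiation or reduction, or show whether an ISI effect is facilitation in one window or suppression in another. The scale argument needs no distributional assumption; it requires only that the compared cells are conditioned ones, which is all the plan states. The rejection rates rest on the assumed variances, number of ISIs and effect sizes. For hypothesis 1.2 and the blocking hypothesis the finding is narrower: no conditioned-versus-unconditioned comparison is stated. The power above 80% at n = 10 belongs to the ANOVA. Neither reading of 0.4 gives 80% at n = 10 for the direct contrast.

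**What to change.** Make this the primary Aim 1 analysis:

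- **TMS and H-reflex amplitudes.** Average the pulses per condition, take each subject's log ratio of conditioned to unconditioned mean, and test it against 0 with a group term. Report back-transformed ratios with confidence intervals. Use the protocol's windows: 2-20 and 20-60 ms for hypothesis 1.1, with 20 ms assigned to one of them since both include it, and up to 50 ms for hypothesis 1.3. Apply Holm across windows. Per-ISI contrasts against unconditioned with multiplicity control are an acceptable alternative.
- **Persistence.** Test the within-subject difference, conditioned minus unconditioned, in percent of 25 pulses: ISIs up to 50 ms for hypothesis 1.2, up to 10 ms for blocking.
- **Name in advance** the CES intensities and pulse pattern entering each test. The two statements of hypothesis 1.3 need reconciling: Section 1 restricts it to subthreshold CES ("Conditioning subthreshold CES will reduce spinal motor neuron H-responses to afferent stimulation over the median nerve"), Section 3 does not. A three-pulse burst at 50 Hz spans 2 × 20 = 40 ms, so say from which pulse the ISI is counted.
- **Zero amplitudes.** Average absent responses in as zero and set a floor for an all-zero mean.
- **Keep** the planned ANOVA as secondary, say that the stated power refers to it, and restate power for the primary contrast.

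The cost is a few sentences of text, with no new data or visits. The downside is dilution: if only 2 of 4 ISIs in a window respond 1.3-fold, the mean log ratio halves from 0.262 to 0.131, a ratio of 1.14. With CV 0.7, between-subject log-SD 0.3 and window SD 0.15, power at n = 30 for a 1.3-fold effect is about 92%. It is about 70% if SCI facilitation is only 1.15, and about 37% if 2 of 4 ISIs respond. Within one group of 15 it is about 49-79% over CV 0.3-1.0 and window SD 0-0.15.

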CES: CES is performed using two DS7A nerve stimulators or a dual DS8R stimulator (Digitimer) linked to deliver biphasic pulses (1 ms each phase; cathodal first). The cathode is a 5x10 cm surface electrode (Natus) placed longitudinally with the top edge ~2.5 cm caudal to the C7 spinous process (~T1-T3 vertebral levels posteriorly). The 5 x 10 cm anode is placed horizontally over the thyroid cartilage, corresponding to the C4-C5 levels anteriorly. Two 5x10 cm common ground electrodes are placed over the distal clavicles. Stimulus intensity ranges from 0-80 mA. Motor threshold is determined analogously to the method used in TMS. Blood pressure, heart rate, pulse oximetry, and peak expiratory flow rate are monitored every three minutes.

Peripheral nerve stimulation: Stimulation is delivered using a DS7A or a DS8R nerve stimulator and dual surface electrodes (20 mm apart). M-wave and F-reflex responses are triggered over the median and ulnar

nerves at the wrist, recording over the APB and FDI muscles, respectively. F-wave pulse intensity is ~110-120% of the intensity that results in maximal compound motor action potential (CMAP). H-reflex responses are triggered over the median nerve at the elbow, recording over the FCR muscle. H-reflex pulse intensity will be calibrated to result in H-reflex amplitude ~20-25% of maximal CMAP⁶³. Pulse width is 0.2 ms for M/F wave stimulation and 1.0 ms for H-reflex stimulation.

Timing: Peripheral motor conduction time is calculated using F-wave and M-wave latencies using the formula $(\text{Latency}_M + \text{Latency}_F - 1) \div 2$ ⁶⁴. Central motor conduction time is calculated as the TMS-evoked potential latency minus the peripheral conduction time. These values are used to precisely synchronize arriving TMS, CES, and peripheral pulses at cervical motor neurons in the relevant experiments.

Replication: For Aim 1, testing will occur over three sessions. For Aim 2, testing will occur over two sessions. This will allow confirmation of key intensity and timing parameters defined for each subject over different sessions, improving reliability of the findings.

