Interpretation: Confirmation of Hypothesis 2.1 would substantiate the predicted findings of Hypotheses 1.1 and 1.2 and our early preliminary data that indicate CES’s ability to positively modulate corticospinal and/or motor neuron excitability. We expect optimal facilitation when subthreshold CES is delivered at closer to motor threshold intensity. We do not know whether the effects will differ depending on intensity of volitional effort, but if so, further experiments could investigate the roles played by peripheral, spinal, and supraspinal components of effort intensity⁶⁹. Furthermore, these experiments would shed light on whether CES modulates ongoing motor neuron activity differently at different spinal levels during level-specific motor tasks (thumb-finger opposition C8-T1, wrist extension C6). Most importantly, confirmation of Hypothesis 2.1 would represent an opportunity to directly translate and test this paradigm for clinical benefit by combining repetitive subthreshold CES with repetitive task-oriented physical exercise training.

If high-intensity CES inhibits concurrent volitional activity as predicted by Hypothesis 2.2, this would be analogous to the ‘cortical silent period’ (CSP) noted when cortical TMS is delivered during volitional contraction^{5,6}. The early phase of CSP (the first 50-75 ms after onset of the cortical motor-evoked potential) is mediated by poorly understood spinal mechanisms⁵. Our observations of the onset and duration of a ‘spinal silent period’ (SSP) in response to CES would shed mechanistic light on this phenomenon.

Aim 2 Data analysis: Rather than peak-to-peak amplitude, the effects of CES on concurrent volitional muscle contraction will be measured using RMS as described above. Repeated-measure ANOVA with factors of subject group, volitional effort intensity, CES intensity, post-stimulus timebin, and muscle will be performed. Post hoc pairwise comparisons will be made using Tukey’s method. Although we can only speculate on the predicted effect size, with use of a conservative effect size of 0.4 for each interaction paradigm, >80% power will be achieved with a sample size of 10 for each analysis (repeated measure ANOVA with five factors). 15 subjects in each group (SCI, able-bodied) will undergo testing.

Aim 2 Timeline:

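### None of the five numbered hypotheses is tied to an ANOVA term or contrast, and the only error control named is Tukey for post hoc pairs

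*Combined protocol and SAP*

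**What the plan says.** Section 3, Aim 1 data analysis, normalizes the peak-to-peak amplitude of conditioned pulses to that of unconditioned pulses and then states: "For each interaction paradigm, analysis of variance (ANOVA) with factors of subject group, stimulus intensity, interstimulus interval, and muscle will be performed". Aim 2 Data analysis states: "Repeated-measure ANOVA with factors of subject group, volitional effort intensity, CES intensity, post-stimulus timebin, and muscle will be performed". Both paragraphs add "Post hoc pairwise comparisons will be made using" Tukey's method. Neither gives a significance level, a primary outcome or term, a list of terms to be read, or a rule across terms, paradigms or Aims.

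The same section numbers five directional hypotheses:
- H1.1: subthreshold CES potentiates the response to TMS.
- H1.2: CES raises F-wave persistence up to 50 ms later.
- H1.3: CES reduces H-reflex amplitude up to 50 ms later.
- H2.1: subthreshold CES facilitates volitional activity.
- H2.2: high-intensity CES inhibits it.

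A further speculative hypothesis predicts that suprathreshold CES blocks F-responses up to 10 ms later.

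Power is given per analysis, not per hypothesis: "Using a conservative predicted effect size of 0.4 for each interaction paradigm", then ">80% power will be achieved with a sample size of 10 for each analysis (repeated measure ANOVA) with four factors". The Aim 2 paragraph repeats this with five factors: ">80% power will be achieved with a sample size of 10 for each analysis (repeated measure ANOVA with five factors".

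**The concern.** The hypotheses and the models do not meet. A reader of the plan cannot say which F test or contrast would decide any of the five hypotheses, so the choice can be made after the results are known. Three features make this more than missing detail.

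- **Aim 1 amplitudes.** Once the outcome is a ratio to the unconditioned response, H1.1 and H1.3 concern the level of that ratio relative to 1. Terms for group, intensity, interval and muscle test whether the ratio varies between conditions. A uniform facilitation of every condition would leave all of them null.
- **H1.1 has no single window.** Conditioning may fall anywhere within 300 ms. The interpretation paragraph attaches one mechanism to facilitation at 2-20 ms and another to 20-60 ms.
- **Aim 2.** CES ranges from sham at 0% to 175% of motor threshold. H2.1 and H2.2 predict opposite effects in different parts of that range. A significant intensity term, or intensity-by-timebin term, does not say which is supported.

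The interpretation paragraphs use the language of confirmation, and for H2.1 they point to a follow-on clinical test. At stake is whether a result described as confirming a hypothesis comes from a test fixed in advance.

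**Working it through.** **The plan's own figure.** The documents state no family-wise error rate. Their only figure is power above 80% with n = 10 and effect size 0.4. Alpha, the correlation and the number of repeated measurements are not given, so it cannot be reproduced from the stated inputs alone. Reading 0.4 as Cohen's f, with one group, N = 10, m = 4 measurements, correlation 0.5 and alpha 0.05, the noncentrality is f²Nm/(1 - ρ) = 0.16 × 10 × 4 / 0.5 = 12.8, and power is 80.6%. With correlation 0 it is 48.3%. Under either reading the figure belongs to a generic repeated-measures effect, not to one of the hypotheses.

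**Number of terms (full factorial, 2^k - 1).**
- Four factors: 2⁴ - 1 = 15. Five factors: 2⁵ - 1 = 31. Three factors: 2³ - 1 = 7.
- Aim 1 is read here as three paradigms: CES-TMS, CES-F and CES-H. The headings give two (CES-TMS and CES-peripheral nerve), but the second is split in its methods: "until 8 (CES-H combinations) or 25 (CES-F combinations) responses per parameter have been recorded".
- H-reflexes come from one muscle ("H-reflex responses are triggered over the median nerve at the elbow, recording over the FCR muscle"), so the muscle factor drops out there.
- Total: 15 + 15 + 7 + 31 = 68. If CES-H kept four factors, it would be 76.

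**Chance of at least one false positive, 1 - (1 - α)^k.** Assumptions: independent tests, every null true, every term read. The documents give no alpha, so 5% is an assumption and 1% is shown beside it.

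| Family | k | α = 5% | α = 1% |
|---|---|---|---|
| One four-factor ANOVA | 15 | 53.7% | 14.0% |
| Five-factor ANOVA | 31 | 79.6% | 26.8% |
| All terms | 68 | 96.9% | 49.5% |
| All terms, CES-H with four factors | 76 | 98.0% | 53.4% |
| One test per numbered hypothesis | 5 | 22.6% | 4.9% |

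For the 68 terms at 5%, 68 × 0.05 = 3.4 false positives are expected. Simulated null mixed ANOVAs (15 per group, assumed numbers of levels, compound symmetry) gave 53.7% for four factors and 79.7% for five, so independence is a fair approximation within one ANOVA.

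**Only terms that contain CES intensity or interstimulus interval.** Group, muscle and group-by-muscle fall out of each four-factor ANOVA, leaving 12. Group falls out of CES-H, leaving 6. Half of the 32 factor subsets in Aim 2 contain CES intensity, giving 16. The total is 12 + 12 + 6 + 16 = 46, and 1 - 0.95⁴⁶ = 90.6%.

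**Power for a named contrast.** Two-sided one-sample t on within-person differences, all 30 participants, noncentrality d√30. Holm's strictest step is 0.05/5 = 0.01 for five contrasts and 0.05/6 = 0.0083 for six.

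| Effect (SD of differences) | α = 0.05 | 0.01 | 0.0083 |
|---|---|---|---|
| 0.8 | 99% | 94% | 93% |
| 0.5 | 75% | 50% | 47% |
| 0.4 | 56% | 31% | 28% |

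The documents give no effect size on this scale; their 0.4 has no named metric.

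**The case against.** The strongest reply is that the hypotheses already narrow what will be read. They are directional and specific. A significant group, muscle or group-by-muscle term supports none of them, so the chance of falsely confirming a hypothesis is not the chance of any significant term. This stands: at an assumed 5%, five hypothesis-level tests give 23%, not 97%. It does not close the gap, because those five tests are not identified in the plan.

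The complete null is also unrealistic. Section 3 refers to a CES-evoked potential, and Aim 2 goes up to 175% of threshold, so evoked responses can fall inside the 200 ms RMS window. CES intensity, timebin and their interaction may then be non-null for that reason alone. The preliminary data report distal muscle selectivity. With fewer true nulls, the 80% and 97% come down.

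A reader might infer that every main effect and interaction will be interpreted at 5%, that Tukey applies only inside a factor, and that some false circuit interaction is therefore almost certain. The documents do not say this. They state no alpha, do not say which terms will be read, and do not define Tukey's family. Near-certainty needs all four ANOVAs pooled, every null true, every term read and an assumed 5%.

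Finally, this is a mechanistic mapping study, and the plan envisages translating and testing the H2.1 paradigm, not claiming benefit from these data. That argues for a modest request, which the one below is.

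**Conclusion.** The point holds as a gap in specification, not as a prediction of false findings. No numbered hypothesis is tied to a term or contrast, no alpha is stated, and error control is named only for post hoc pairs. For H1.1 and H1.3 the listed factors do not test the hypothesis directly unless the unconditioned state is added as a level. That conclusion needs no assumption about alpha or independence.

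The error rates (54%, 80% and 97%, or 50% over 68 terms at a 1% level) are upper-end figures. They rest on a full factorial in each ANOVA, the reading of Aim 1 as three paradigms, independence, a complete null and the reading of every term. The lower reference point is 23%. Separate analyses of silent-period duration, or of single pulses and theta bursts, would raise the count of terms. The correction should be made before the data are analysed.

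**What to change.** In the Aim 1 and Aim 2 data analysis paragraphs, name a directional contrast for each hypothesis: conditioned versus unconditioned in Aim 1, CES versus sham in Aim 2. Restrict each to the intensity and interval its hypothesis concerns, and state the outcome and the muscles, effort levels and time bins it covers.

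- **H1.1:** subthreshold, with 2-20 ms and 20-60 ms as separate contrasts, because they carry different mechanisms.
- **H1.2:** F-wave persistence up to 50 ms, kept apart from the suprathreshold, up-to-10 ms condition in which the speculative hypothesis predicts block. Averaging the two would mix opposite predictions.
- **H1.3:** subthreshold, as in the Specific Aims, up to 50 ms.
- **H2.1:** subthreshold.
- **H2.2:** suprathreshold, with the analysis range fixed before data are seen, since high intensity has no numeric definition.

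State alpha. Label every other ANOVA term and post hoc comparison exploratory, and do not describe any of them as confirming a hypothesis.

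Holm across the named contrasts is optional. Its cost depends on the effect: for five contrasts, power at the strictest step is 94% against 99% unadjusted at 0.8 SD, 50% against 75% at 0.5 SD, and 31% against 56% at 0.4 SD. Splitting H1.1 makes six contrasts and takes one to three points more. If Holm is not used, the plan should say that the contrasts are unadjusted.

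No new participants, visits or measurements are needed. The cost is analysis text plus the decisions on windows and ranges, which have to be made and recorded before analysis.
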